8.2. Adverse Events

All AEs will be classified by system organ class (SOC) and preferred term, according to a standardized thesaurus (Medical Dictionary for Regulatory Activities [MedDRA] version 24.0). The severity of non-allergic AEs will be classified using the FDA Guidance for Industry Toxicity Grading Scale for Healthy Adult and Adolescent Volunteers Enrolled in Preventive Vaccine Clinical Trials (September 2007), and the severity of systemic allergic reactions will be graded using CoFAR Grading Scale for Systemic Allergic Reactions Version 3.0. Each AE is entered on the electronic case report form (eCRF) once at the highest severity. As such, no additional data manipulation is needed to identify events.

An overall summary table will be developed to report the number of events and the number and percentage of participants having at least one event in the following categories:

- AEs
- AEs indicated as systemic allergic reactions

- AEs that lead to study treatment discontinuation
- AEs indicated as serious
- AEs with an outcome of death
- AEs that were reported as being related to vaccine/placebo
- AEs reported by severity

In addition, AEs classified by MedDRA SOC and preferred term will be summarized for each treatment group and overall.

Summary tables will present the total number of events as well as the number and percentage of participants experiencing the events. If a participant experiences the same AE on multiple occasions, the event will be counted once for each occurrence when reporting the number of AEs. When reporting the number of participants experiencing the events, a participant will only be counted once if they experience an event within the particular SOC or preferred term.

Percentages will be based on the number of participants in the safety population.

In addition, treatment-emergent AEs classified by MedDRA SOC and preferred term will be summarized for each treatment group, cohort assignment (HA/MCD or Comparison), and overall. The proportion of participants in each study arm experiencing each type of AE will be compared using a Fisher's Exact test. The frequency of treatment-emergent AEs will also be summarized by SOC and preferred term for severity (grade) and relationship to study treatment.

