#### 3.5.2. Blinding/Masking and Planned Unblinding

An unblinded pharmacist will prepare each vaccine, and an unblinded qualified medical professional will administer the vaccine in such a way that the participant cannot see the syringe. Unblinded staff may also schedule study visits and conduct procedures other than clinical endpoint assessments. Staff performing clinical assessments will not know whether a participant is receiving placebo or vaccine, or which vaccine a participant is receiving at the first visit. During a follow-up call, scheduled 3 days after the first vaccination/placebo dose, participants will be scheduled for their next dose.

Under protocol versions 1.0 - 4.0, participants and the staff were unblinded during the follow-up call 3 days after the second injection when a third appointment (for those who received a placebo injection first) was, or was not (active vaccinations only) scheduled. Due to the different dosing schedules for the Pfizer-BioNTech COVID-19 Vaccine and Moderna COVID-19 Vaccine, it became apparent to both the site staff and study participant which vaccine had been assigned, once their second injection was scheduled.

Under protocol versions 5.0 – 8.0, the participant, their parents/legal guardians, and staff will be aware of whether a participant received placebo at the phone call 3 days after the first injection when the participant is scheduled for the first active vaccine in approximately 7 days after placebo. Participants, their parents/legal guardians, and staff will not be blinded to vaccine assignment as only one active vaccine will be implemented at a given time.

Vaccination reports to the state and local authorities will be completed after a participant is unblinded.

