### **8.5. Participants Randomized to Receive Placebo**

#### **8.5.1. First Vaccination Visit (Day 22 or 29; -4 to + 14 Days)**

Participants randomized to placebo will be asked to return to clinic to receive their first vaccine injection, approximately 21 or 28 days, per vaccine assignment, after they received the placebo. In addition to receiving the Pfizer-BioNTech COVID-19 Vaccine or Moderna COVID-19 Vaccine, the participant will complete the same study procedures as those conducted during the Enrollment Visit, with the exception of growth parameters (Section 8.2 Enrollment Visit [Day 1]).

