## 13.4. Collection and Recording of Adverse Events

### 13.4.1. Collection Period

Adverse events will be collected from the time of consent, until a participant completes study participation or until 7 days after their last vaccine dose after he/she prematurely withdraws (without withdrawing consent) or is withdrawn from the study if the participant received study treatment (vaccine or placebo).

AEs will be recorded during the periods defined below.

- **Solicited AEs:** Those occurring within 7 days of each injection (vaccine or placebo), inclusive of the injection day
- **Unsolicited AEs:** Those occurring from the time of consent through study participation

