Study Duration	
Participant Vaccination and Follow-up:
 
Participants randomized under protocol versions 1.0 - 4.0: Randomized and vaccinated participants will complete study participation in approximately 29 days if vaccinated with the Pfizer-BioNTech COVID-19 Vaccine, 36 days if vaccinated with the Moderna COVID-19 Vaccine, and 50 or 64 days if administered placebo before receiving two doses of either the Pfizer-BioNTech COVID-19 Vaccine or the Moderna COVID-19 Vaccine, respectively.
 
Participants randomized under protocol versions 5.0 – 8.0: Randomized and vaccinated participants who receive both doses of vaccine will complete study participation in approximately 29 days if vaccinated with the Pfizer-BioNTech COVID-19 Vaccine, 36 days if vaccinated with the Moderna COVID-19 Vaccine, and 36 or 43 days if administered placebo before receiving two doses of either the Pfizer-BioNTech COVID-19 Vaccine or the Moderna COVID-19 Vaccine, respectively.

Treatment Description	Each participant will receive 2 doses of either the Pfizer-BioNTech COVID-19 Vaccine or the Moderna COVID-19 Vaccine. Participants randomized to placebo, will receive a placebo dose before receiving 2 doses of either the Pfizer-BioNTech COVID-19 Vaccine or the Moderna COVID-19 Vaccine.

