4. ANALYSIS SAMPLES

As-treated sample: All participants who are randomized and receive at least one active vaccination for any active injection analysis or all participants who are randomized and receive a placebo for any placebo injection analysis. Participants will be analyzed according to the vaccine they received.

Per-Protocol sample: All participants who are randomized and receive all assigned vaccination doses. Participants who do not receive a second active vaccination due to experiencing an allergic reaction will be included in the analysis. Participants will be analyzed according to the vaccine they received.

Safety sample: All participants who consent and undergo screening procedures. Participants will be analyzed according to the vaccine they actually received, regardless of the treatment arm to which they were randomized. Non-treatment emergent adverse events (e.g., any adverse event that occurs before the first injection) will be summarized in all participants in the safety sample, while treatment-emergent adverse events (e.g., any adverse event that occurs on or after the first injection) will be summarized in the subset of participants who receive an injection (placebo or active vaccination).

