6.2. Treatment Adherence

Participants in the Pfizer-BioNTech COVID-19 Vaccine and Moderna COVID-19 Vaccine treatment arms will receive two injections, while those in the placebo + Pfizer-BioNTech COVID-19 Vaccine and placebo + Moderna COVID-19 Vaccine treatment arms will receive three injections.

Treatment adherence will be summarized by treatment group within each cohort and overall. Study treatment administration data will be listed by treatment group, cohort (HA/MCD or Comparison) and participant.

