    ((dose = 'D1' & Placebo = 'Yes') | (dose = 'D2' & Placebo = 'No'));
  class dose;
  model resp(event = '1') = dose / dist=binomial link = logit;
  lsmeans dose / e ilink diff exp;
  store out=genmod;
  ods output coef = coeffs;
run;
%NLMeans(instore=genmod, coef=coeffs, link=logit, title= Priming Prop
Diff);
```

Handling of Missing Data

Participants with missing data for their 2nd active dose for reasons other than systemic allergic reactions in their 1st active dose will be removed from this analysis (complete case analysis).

Participants with missing data for their 2nd active dose because of a systemic allergic reaction to their 1st active dose (inherent missingness given the current design) will be examined using an extreme case scenario (replacement of all 2nd active dose missing by either yes or no). If the result from this extreme case scenario differs and if there is at least 10 systemic allergic reactions in the 1st active dose a tipping point analysis will be conducted.

Notes

The same analysis will be repeated for the Moderna COVID-19 Vaccine.

7.3.4. Secondary Endpoint 5

Objective (First dose comparison to Placebo)

Assess the proportion of participants with systemic allergic reactions to the Pfizer-BioNTech COVID-19 Vaccine in the HA/MCD after adjusting for placebo

Endpoint

The proportion of participants who experience a systemic allergic reaction (CoFAR Grade 2 and above regardless of tryptase, or CoFAR Grade 1 with elevated tryptase [1.2 x baseline plus 2 ng/ml]) within the 90-minute post-vaccination observation period to the first dose of the Pfizer-BioNTech COVID-19 Vaccine after adjusting for placebo administration

Model Specification

- Endpoint is as defined above.
- Endpoint will be analyzed using Barnard's unconditional exact test.

Model Checking & Diagnostics

This analysis will not be carried out if there are no systemic allergic reactions for the placebo dose.

Model Results Presentation

Proportion difference, 95% exact unconditional confidence interval and p-value will be presented for the comparison between 1st dose (active arm) and placebo dose (placebo arm)

Placebo + Pfizer-BioNTech/Placebo + Moderna COVID-19 Vaccine (**placebo**) vs Pfizer-BioNTech COVID-19 Vaccine (**1st**)

Placebo + Pfizer/Placebo + Moderna	placebo	1st	2 nd
Pfizer	1 st	2 nd	

SAS Code

```
*** 1st dose comparison to Placebo;
proc freq data = d_1;
  title "1st dose comparison to Placebo";
  where group = 'HA/MCD' &

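### The adverse-event tests in SAP 8.2 compare arms with different numbers of injections and lengths of follow-up, with no common window

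*SAP*

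**What the plan says.** SAP 8.2 summarises treatment-emergent adverse events by system organ class and preferred term. A participant counts once per term, and a test is added: "The proportion of participants in each study arm experiencing each type of AE will be compared using a Fisher's Exact test". Study arm is not defined there.

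Four other places fix the exposure behind that comparison:

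- SAP 4 defines treatment-emergent as "any adverse event that occurs on or after the first injection". The first injection may be placebo, and no end point is given.
- Protocol 13.4.1 collects solicited events for 7 days after each injection. Unsolicited events are "Those occurring from the time of consent through study participation".
- SAP 6.2 gives the vaccine-only arms two injections, "while those in the placebo + Pfizer-BioNTech COVID-19 Vaccine and placebo + Moderna COVID-19 Vaccine treatment arms will receive three injections".
- SAP 1 (Study Duration) gives versions 1.0-4.0 about 29 days (Pfizer-BioNTech) or 36 days (Moderna) without placebo, and "50 or 64 days if administered placebo before receiving two doses" with it. Under versions 5.0-8.0 the placebo-first figures are 36 or 43 days.

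The per-dose rates in SAP 7.2.4 and the first-dose v placebo contrast in SAP 7.3.4 cover systemic allergic reactions only. Nothing in SAP 8 supplies an equal-window, per-injection or exposure-adjusted comparison for general adverse events.

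**The concern.** An ever/never proportion grows with observation time and number of injections. Here both differ by design between the vaccine-only and placebo-first arms. Over the whole study the placebo-first arm is also not a placebo control, because its participants go on to receive both active doses.

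Two errors follow. Background events can appear in excess in the placebo-first arms only because those participants were watched longer. A real excess after active vaccine can disappear, or appear reversed, because both arms carry the same two active doses and one has a further saline injection and more days. The tables would be read as evidence on vaccine safety in allergic patients, so the wrong reading matters even though no stopping or decision rule uses these tests.

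**Working it through.** **1. Follow-up from the schedule (versions 1.0-4.0).** End of study is the day of the last vaccination plus 7 (Protocol 8.4.1, 8.5.3, 8.6).

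| | Vaccine-only | Placebo-first | Extra days |
|---|---|---|---|
| Pfizer-BioNTech | 22 + 7 = 29 | 43 + 7 = 50 | 21 |
| Moderna | 29 + 7 = 36 | 57 + 7 = 64 | 28 |

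These match the stated durations. Solicited collection is 2 x 7 = 14 v 3 x 7 = 21 days. Under versions 5.0-8.0 the gap is 36 - 29 = 43 - 36 = 7 days.

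**2. Assumptions.** The SAP sets no alpha for these tests, and the documents give no background event rates for this trial. I assume two-sided 0.05. For size I put all 3400 participants under 2:2:1:1: 3400 x 2/6 = 1133 v 3400 x 1/6 = 567 per vaccine. This is an upper bound, since versions 5.0-8.0 use 2:1. For HA/MCD alone (1020 per vaccine) it is 680 v 340; for the comparison group (680) it is 453 v 227.

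**3. Background events, no vaccine effect.** With a constant hazard and risk p1 in the vaccine-only arm, the placebo-first risk is p2 = 1 - (1 - p1)^(50/29) for Pfizer-BioNTech and 1 - (1 - p1)^(64/36) for Moderna. At p1 = 5%, p2 is 8.5% and 8.7%. Rejection probabilities of Fisher's test, by exact enumeration:

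| p1 | 0.5% | 2% | 5% | 10% |
|---|---|---|---|---|
| Pfizer-BioNTech, 1133 v 567 | 14% | 39% | 77% | 97% |
| Moderna, 1133 v 567 | 15% | 44% | 82% | 98% |
| Pfizer-BioNTech, 680 v 340 | 10% | 25% | 54% | 83% |
| Moderna, 680 v 340 | 11% | 28% | 60% | 88% |
| Pfizer-BioNTech, 453 v 227 | 8% | 18% | 39% | 66% |
| Equal exposure, 1133 v 567 | 3.3% | 4.0% | 4.4% | 4.5% |

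Counting days elapsed since Day 1 (28 v 49) instead of study days changes little: 79% at 5% and 97% at 10% for Pfizer-BioNTech.

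**4. Other readings of study arm.** One four-arm test (1133/1133/567/567 at 29/36/50/64 days) rejects in about 24/71/98/>99% at 0.5/2/5/10% incidence by day 29. This used simulation with a chi-square approximation to the exact test. Pooled by vaccine (1700 v 1700), simulation gives 6/18/40/67%, because Moderna follow-up is longer.

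**5. Events mainly from the active doses.** With risk d per active dose and s after saline, compare 1 - (1 - d)^2 with 1 - (1 - d)^2 (1 - s) at 1133 v 567. The active-dose risk is the same in both arms.

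| d, s | Vaccine-only | Placebo-first | Rejection |
|---|---|---|---|
| 5%, 1% | 9.75% | 10.65% | 8% |
| 20%, 2% | 36.0% | 37.3% | 8% |
| 30%, 5% | 51.0% | 53.5% | 15% |

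**6. Masking.** Take a 7-day risk of 5% after active vaccine and 2% after saline. Whole-study proportions are 1 - 0.95^2 = 9.8% v 1 - 0.95^2 x 0.98 = 11.6%.

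| Sizes | Planned test: vaccine-only higher | Planned test: placebo-first higher | 7-day first-injection test detects the excess |
|---|---|---|---|
| 1133 v 567 | 0.1% | 20% | 88% |
| 680 v 340 | 0.2% | 13% | 65% |
| 453 v 227 | 0.3% | 10% | 45% |

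**7. Children, versions 5.0-8.0.** With 300 children at 2:1 (200 v 100) and 29 v 36 days, rejection is 5/6/8% at p1 = 2/5/10%.

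**The case against.** The strongest reply is that the large figures rest on favourable assumptions. They need background events, constant hazard, full enrolment under versions 1.0-4.0 and merged cohorts, whereas SAP 8.1 and 8.2 split displays by age group and cohort. Many vaccine-trial events are dose-driven. Protocol 5.1 lists injection-site pain at 84.3% and fatigue at 51.7% from another study in children. Solicited events are collected for only 7 days per injection, so for them the imbalance is one extra diary week after saline, not 21 or 28 days. Rarer terms (0.1-0.2%) are barely affected: 3-8% rejection at full size for Pfizer-BioNTech. If arms are pooled by vaccine, the extra-injection imbalance cancels at 2:1. The DSMB also receives listings by vaccine arm/placebo and population, events are tabulated by relationship, and general adverse events are not a study objective.

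This limits the size. The inflation is modest for dose-driven and rare events and small in children, and cohort-level figures are lower than the full-size ones. It does not remove the defect. The direction of the bias does not depend on the rates. Pooling by vaccine is not stated, would leave no placebo contrast, and still leaves unequal Pfizer-BioNTech and Moderna follow-up. Listings and relatedness tables do not correct a test the SAP prescribes for every event type. Deleting the Fisher sentence would also remove the misreading, but would leave no active v placebo comparison of general adverse events.

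**Conclusion.** The concern holds. As written, SAP 8.2 tests cumulative adverse-event proportions between an undefined set of arms whose exposure under versions 1.0-4.0 differs by one injection and 21 or 28 days. For background events with 2-10% risk in the vaccine-only arm, false rejection runs from 25% to 88% in HA/MCD alone and from 39% to 98% at the upper-bound size, against about 4% with equal exposure. In the masking example the planned test is far more likely to point the wrong way than the right way at every size examined. These sizes depend on the assumed alpha, event rates, hazard and enrolment.

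The scope is general adverse events only. The 90-minute allergic-reaction endpoints, including the placebo-adjusted endpoint in SAP 7.3.4, are not affected. The change should be made, but it does not touch the primary conclusions.

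**What to change.** In SAP 8.2:

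1. Define study arm and state which arms are contrasted.
2. Limit Fisher's tests of active v placebo-first to treatment-emergent events in a common window after the first injection.
   - Versions 1.0-4.0: 7 days including the injection day, censored in both arms at the next injection. The earliest scheduled next injection is Day 22 - 4 = Day 18 (Protocol 8.4.1, 8.5.1), so the windows do not overlap. The comparison is also largely blinded, since "participants and the staff were unblinded during the follow-up call 3 days after the second injection" (Protocol 3.5.2). The exception is participants unblinded after the day 4 diary review under Protocol 3.6.
   - Versions 5.0-8.0: up to the call 3 days after the first injection, before placebo status is disclosed and before any second injection. A 7-day window is not safe here. Protocol 9.3, 9.5.1 and Appendix 3 Table D disagree on how early the next injection may fall, and these must be reconciled.
3. Tabulate later events by active dose, with recipients of that dose as the denominator.
4. Keep whole-study by-arm tables descriptive. Pfizer-BioNTech v Moderna tests may stay if made over equal post-dose windows.

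The cost is SAP wording and a date filter on event and injection dates already collected. Events outside the window are described, not tested, between active and placebo-first arms, so delayed events get no formal placebo comparison; the present test does not isolate them either. In children the windowed test will be weak: at 200 v 100, even a full 7-day contrast of 5% v 2% is detected in only 16% of trials, and the proposed window is shorter.

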8.3. Deaths and Serious Adverse Events

Serious adverse events (SAEs) will be listed and summarized in the same manner described in Section 8.2. Separate displays listing and summarizing death, including time to death and cause of death, will also be created.

8.4. Clinical Laboratory Evaluation

Clinical laboratory measurements include hematology. Results will be converted to standardized units where possible. Descriptive statistics of laboratory values and the change from baseline of laboratory values will be presented for each treatment group and overall.

Laboratory data will be plotted to show patterns over time. Data will be plotted as a spaghetti plot where each participant's values will be plotted and connected by line segments, forming one line per participant. Quantile plots with treatment group means (or medians) as well as 25th and 75th percentiles plotted over time will be created.

All data mentioned above will also be summarized by those with and without allergic reactions.

8.5. Vital Signs, Physical Findings, and Other Observations Related to Safety

8.5.1. Vital Signs

Descriptive statistics of vital signs results and change from baseline of vital signs will be summarized for each treatment group and overall. Data listings sorted by treatment group, participant, vital sign parameter, and time of assessment will be provided for vital signs measurements.

8.5.2. Physical Examinations

Physical examination results of normal, abnormal, and not done will be summarized as frequencies and percentages by body system and visit. Data listings will be provided for

physical examination results and sorted by treatment group, participant, body system, and time of assessment.

9. OTHER ANALYSES

9.1. Use of Medications

Medications will be coded according to the World Health Organization (WHO) Drug Dictionary (version 2021-MAR). Medications reported on the CRF will be categorized for analysis as prior, concomitant, or after study treatment by comparing the medication start and stop dates with the first and last dose of study treatment dates. Prior medications will have both the medication start and stop dates prior to the first dose of study treatment date. After medications will have both the medication start and stop dates after the last dose of study treatment date. All other medications will be classified as concomitant, indicating that use of the medication overlapped with use of the study treatment by at least one day.

The number and percentage of participants receiving prior, concomitant, and after medications will be presented overall and by medication class. When reporting the number of participants receiving the medication, a participant will only be counted once if they ever received the medication within the medication class. Percentages will be based on the number of participants in the safety sample.

10. INTERIM ANALYSES AND DATA MONITORING

The progress of the study will be monitored by the Data and Safety Monitoring Board (DSMB). The DSMB will be chartered to review safety data and to make recommendations regarding continuation, termination, or modification of the study. The DSMB will formally review the safety data when planned milestones for randomization/first vaccination are reached (approximately every 500 participants complete their vaccination schedule). Unblinded data for the planned safety reviews will include, at a minimum, a listing of all reported AEs and SAEs by vaccine arm/placebo and population. Outcome data will show the counts, proportions (with corresponding 95% CI), and difference in proportions between the HA/MCD and comparison group within each vaccine (with corresponding 95% CI) of the primary and key secondary endpoints. Interim p-values will be available upon request. Data may be reviewed and discussed via email or by teleconference. The DSMB may recommend continuing the study, modifying the study, stopping the study, and/or announcing information while the study is still ongoing.

In addition, safety data will be reviewed by the DSMB when an event occurs that is of sufficient concern to the National Institute of Allergy and Infectious Diseases (NIAID) medical monitor or protocol chair to warrant review, or when an event occurs that could contribute to a predefined stopping rule specified in the protocol.

Findings will be reported to Institutional Review Boards (IRBs) and health authorities.

